## 10.0 COMPANION STUDIES

There will be 1 mandatory imaging companion for patients whose disease is being monitored by MRI. There will also be 2 optional sub-studies: A091105-HO1 (Health Outcomes) and A091105-ST1 (Correlative Science). A091105-HO1 and A091105-ST-1 must be offered to all patients for their consent, although patient participation is optional.

### 10.1 Imaging companion study incorporated within A091105: Evaluation of MRI T2 signal as a novel imaging biomarker in DT/DF treated with sorafenib

#### 10.1.1 Objectives

In a retrospective study, DT/DF patients treated with sorafenib demonstrated decrease in MRI T2 signal intensity suggesting a decrease in cellularity. In this prospective trial, we will undertake exploratory studies to test whether MRI T2 changes can predict (or correlate) with a biological response such as RECIST response, and pain palliation (for patients whose disease is being monitored by MRI).

#### 10.1.2 Methods

Methods Study:

The goal of the MRI portion of this study is to assess the T2-weighted sequences to determine the percentage of the entire tumor volume that is hyperintense relative to normal muscle at baseline compared with follow-up examinations. The patient will undergo an MR examination on a 1.5 T (or greater) whole body scanner located at one of the participating institutions. T2-weighted MR images with fat-saturation will be obtained with standard fast spin-echo pulse sequences with the following sequence parameters: TR = 4000-6600ms, TE = 60-70 ms, echo-train length = 24, number of slices = 30, 4-5 mm thickness, FOV = 320 mm, matrix size = 256x192. If adequate fat saturation cannot be achieved due to the location of the tumor, metal artifacts or patient positioning, the patient will be excluded from T2-signal analysis portion of this study. STIR may be performed but cannot replace T2 with fat saturation in the data analysis for the purpose of this research.

**Analysis of the data** will be performed in two phases: semi-quantitative and quantitative analysis. All images (DICOM compatible with sensitive patient information de-identified) will be analyzed by two reference radiologists and a physicist from Memorial Sloan-Kettering Cancer Center. In phase one, a reference radiologists will review the images in regions suspicious of desmoid to measure changes in signal intensity for clinical assessment. A region-of-interest (ROI) is drawn to include the entire tumor at its greatest cross-sectional diameter. The ratio of mean ROI tumor signal intensity to the signal intensity of an ROI on the adjacent skeletal muscle is calculated. In the second phase, images will be analyzed to quantify the loss of MRI T2 signal intensity using a histogram analysis.

The Alliance Statistics and Data Center A091105 Statistician will prepare analysis datasets in conjunction with clinical/outcome data. Analyses will be coordinated by the A091105 Statistician and conducted using the analysis datasets used for the analysis of the clinical endpoints to ensure consistent data is reported for the primary and secondary endpoints (e.g. data associated with censoring, proper inclusion of crossover data, and data to be excluded in cases of consent withdrawals for follow-up and correlative studies).

**DW-MR images** will be obtained by using a spin-echo echo-planar imaging (SE-EPI) sequence with a pair of rectangular-shaped gradient pulses along three orthogonal axes. Imaging parameters are TR = 4000-5475ms, TE = 77.6–110.3 ms, FOV = 320 mm, 4-5 mm thickness, no inter-slice gap; b-values were 0, 400, and 700 s/mm^2. The advantage of two non-zero b-values as opposed to one b value is that estimated parameters are less influenced by the choice of b-value and may be more appropriate than ADC for use in multi-institutional studies. The orientation and location prescribed are identical to those prescribed for the transverse T2W images. Four to eight signal averages are obtained for this portion of the exam with an approximate imaging time of 5 - 7 minutes to acquire the two sets of b-values.

**Absolute T2-values** are obtained with a multi echo (dual echo) fast spin echo imaging sequence at 4 different echo times (TEs). TE values will be: 50, 80, 110, 150 ms (there is flexibility in the values acquired to within 10 ms). The acquisition parameters are: TR = 6600 ms; FOV = 320 mm; 4-5 mm thickness; number of signal acquired, one; echo train length, 24; matrix, 256 × 192. The images are acquired at the same location, FOV, and coverage and the DW-MR images. Using a dual echo fast spin echo sequence, two echoes are acquired per sequence with a total of two sequences acquired.

Summary of Histogram analysis: Using custom-made software developed in MATLAB environment (version 7.1, Mathworks, Natick, MA) the 25th and 50th (median) percentile values, kurtosis, and skewness of the ROI histograms are computed. Kurtosis provides a quantitative measure of how sharply peaked a histogram is compared with the histogram of a normal distribution. Accordingly, whereas a normal distribution has a kurtosis of 0, a more peaked histogram has a positive kurtosis value. Skewness provides a quantitative measure of the degree of asymmetry of a histogram: a perfectly symmetric histogram has a skewness of 0; a histogram with a long right tail has a positive skewness, whereas a negative skewness is due to the presence of a long left tail.

## 10.2 QOL Sub-Study-A091105-HO1 (Optional)

There is clinical evidence to suggest that sorafenib improves the quality of life by improving pain and/or decreasing in narcotic drug use. Based on a retrospective review by Gounder et al. (2011), approximately 70% DT/DF patients (16/22) reported subjective decrease in pain and analgesic use after initiation of sorafenib. However, these data were not quantitated using a validated pain scale. Thus, patient-reported outcomes (PRO) will be a key secondary endpoint in this trial, both to assess for improvement in disease-related symptoms/QOL and for impact of sorafenib treatment.

Also, evidence has arisen indicating that baseline single-item assessments of fatigue and overall QOL are strong prognostic indicators for survival in cancer patients, independent of performance status. This evidence was derived from two separate meta-analyses recently presented at ASCO, the first involving 23 NCCTG and Mayo Clinic Cancer Center oncology clinical trials, the second involving 43 clinical trials. Routine inclusion of these measures should be considered similar to that of including performance status, either as stratification or prognostic covariates.

### 10.2.1 Objectives

- To compare pain palliation (primary) and time to pain progression (secondary) between arms using three items from the Brief Pain Inventory Short Form and Pain Medication Diary.
- To compare patient-reported adverse events and QOL between arms as measured by the PRO-CTCAE and the single-item overall LASA.

### 10.2.2 Methods

The following patient assessments will be included in this study:

**Brief Pain Inventory – Short Form:** The Brief Pain Inventory (BPI) is a pain assessment tool used with cancer patients to measure both pain intensity (sensory dimension) and pain interference (reactive dimension) in the patient’s life. The BPI has been validated in >30 different languages across a range of cancer types. To minimize patient burden, only three items will be used from the BPI, the item assessing “worst pain” severity and two items assessing inference with general activity and sleep.

**PRO-CTCAE:** Completed on paper at the following time points: prior to randomization; and every 4 weeks up to Week 32 while on randomized treatment; and at end of randomized treatment.

The PRO-CTCAE is a group of items currently being developed by the NCI for direct patient-reporting of adverse symptoms in cancer trials. To date, 78 symptomatic adverse events in the CTCAE have been developed for patient self-reporting via the PRO-CTCAE, and have undergone refinement in a cognitive testing study. A large validation of the PRO-CTCAE has been completed across various cancer types and is expected to provide comprehensive results in support of validation at ASCO 2012 for items selected for this study. In this study, we will administer PRO-CTCAE items for 11 symptoms pertinent to patients in this trial and in this population: insomnia, constipation, pain, fatigue, nausea, vomiting, diarrhea, rash, hand-foot syndrome, decreased appetite, and mouth or throat sores.

**Single-item overall LASA:** Completed on paper at the following time points: prior to randomization and every 4 weeks up to Week 32 while on randomized treatment; and at end of randomized treatment.

The Linear Analogue Self-Assessment (LASA6) consists of six single-item numeric analogue scales. For this study, we will employ only the one item that measures overall QOL on a scale of 0-10. LASA items such as these have been validated as general measures of global QOL dimensional constructs in numerous settings. The LASA has been validated at the Mayo Clinic for use in cancer patients and have been successfully used in numerous clinical trials. The single-item overall LASA has been shown to be prognostic for survival in a range of cancer types.

• **Pain Medication Diary:** Daily reporting for 7 consecutive days via paper diary prior to randomization, every 4 weeks through Week 32 while on randomized treatment, and at end of randomized treatment. This pain medication diary will be used to quantify opioid narcotic use for computing pain palliation and pain progression.

### 10.2.3 Specific hypotheses

Our primary hypothesis is that pain palliation will be improved on the sorafenib arm as compared to the placebo arm as suggested by the retrospective review by Gounder et al. Our secondary hypothesis is that time to pain progression will be extended on the sorafenib arm as compared to the placebo arm, based on our hypothesis that sorafenib will prolong progression-free survival. To understand the impact of the hypothesized pain improvement associated with sorafenib on patients, pain interference on general activity and sleep will also be compared between arms, where we expect interference in both domains to be improved on the sorafenib arm as compared to the placebo arm. In terms of patient-reported adverse events, we hypothesize that pain and insomnia will be improved on the sorfenib arm as compared to the placebo arm; and that fatigue, gastrointestinal toxicity (constipation, nausea, vomiting, diarrhea, decreased appetite, and mouth or throat sores) and skin toxicity (rash, hand-foot syndrome) will be negatively impacted on the sorafenib arm as compared

to the placebo arm given the adverse event profile of sorafenib in other patient populations and based on the adverse events reported in the retrospective review by Gounder et al. Lastly, given the possibility of improved pain and insomnia at the cost of increased treatment toxicity, we will compare overall quality of life between arms and hypothesize that quality of life will be improved on the sorafenib arm as compared to the placebo arm (i.e., that larger improvement in pain will offset the added toxicity of sorafenib treatment).

The Alliance Statistics and Data Center A091105-HO1 Statistician collaborate with the A091105 Statistician to prepare analysis datasets in conjunction with clinical/outcome data. Analyses will be conducted by the A091105-HO1 Statistician, using the analysis datasets used for the analysis of the clinical endpoints to ensure consistent data is reported for the primary and secondary endpoints (e.g. data associated with censoring, proper inclusion of crossover data, and data to be excluded in cases of consent withdrawals for follow-up and correlative studies).

### 10.3 A091105-ST1 “Analysis of archival tissue, and pre-treatment and day 8 tumor biopsy and blood samples” (Optional)

#### 10.3.1 Objectives

- The mechanism of action of sorafenib in DT/DF remains unknown. All patients will undergo treatment tumor biopsies. Treatment induced changes will be quantified by histology, gene expression profiling, proteomic changes and selected interrogation of key pathways by Western blot and RT-PCR.
- To collect archival tissue, pre-treatment biopsies and blood and day 8 biopsies and blood specimens for basic science research.

Three recurrent mutations in beta-catenin gene have been documented and prognosticate risk of local recurrence after surgery. However, there is no study that has attempted to evaluate whether these mutations are predictive biomarkers of response to sorafenib. We will attempt to answer this question in this prospective study.

#### 10.3.2 Methods

All correlative studies will be performed in the laboratory of [name] (correlative chair). From archival FFPE specimen in patients who consent to A091105-ST1, sections (preferably 40 micron x1 or 20 micron rolls x2, cut from blocks with at least 50% tumor content after review by designated study pathologist) will be prepared by OSU and sent to the [name] laboratory. DNA sequencing will be performed as previously described by Lazar et al. DNA will be extracted from FFPE material using the QIAamp DNA mini kit DNA isolation kit (Qiagen Valencia, CA). Polymerase chain reaction (PCR) will use primers (*BCAT-DES-F*: 5\_-AGTCACTGGCAGCAACAGTC-3\_ and *BCAT-DES-R*: 5\_-TCTTCCTCAGGATTGCCTT- 3) and under thermocycling conditions previously reported to amplify exon 3 of *CTNNB1* (phosphorylation domain, codons 30 to 48) with appropriate controls. PCR products will be detected by gel electrophoresis in 2% agarose, and amplicon bands further purified using the QIAquick gel extraction kit (Qiagen). Direct sequencing used the above primers (forward and reverse), ABI Prism dye terminator cycle sequencing ready reaction kit, and ABI Prism 3100-Avant genetic analyzer (Applied Biosystems, Foster City, CA). Both strands will be analyzed by the NCBI Blast Alignment Tool (<http://www.ncbi.nlm.nih.gov/blast/Blast.cgi>) to identify mutations.

The Alliance Statistics and Data Center A091105 Statistician will prepare analysis datasets in conjunction with clinical/outcome data. Analyses will be coordinated by the A091105 Statistician and conducted using the analysis datasets used for the analysis of the clinical endpoints to ensure consistent data is reported for the primary and secondary endpoints (e.g.

data associated with censoring, proper inclusion of crossover data, and data to be excluded in cases of consent withdrawals for follow-up and correlative studies).

### 10.3.3 Specific hypotheses

DT/DF is sporadic (~85%) or arise in the setting of familial adenomatosis polyposis (4 – 20%) with germline mutations in APC. Sporadic desmoids have mutations in the  $\beta$ -catenin gene (CTBNN1) with certain mutations associated with high local recurrence.  $\beta$ -catenins function both as a cell adhesion molecule and as a transcriptional activator in the presence of Wnt ligand. Mutations in APC or CTBNN1 result in accumulation of nuclear  $\beta$ -catenin and transcriptional activation of growth signals including Tcf, *c-MYC*, *c-JUN*, and *cyclin D* (Figure 6). Carcinomas that over-express CTNNB are associated with an indolent disease with lack of metastatic ability. Sorafenib is a multi-kinase inhibitor that targets B-Raf, PDGFR- $\beta$  and VEGFR-2/-3. Both c-KIT and PDGFR-B has been shown to be over-expressed in DT/DF without any underlying mutations. In clinical trials of imatinib in DT/DF, extensive search for tumor or serum biomarkers of response were unsuccessful. Response in DT/DF are thought to involve a shift from fibroblast to collagen deposition and fibrosis. We hypothesize that differences in histology, protein and gene expression patterns in paired tumor biopsies identify critical pathways that are transcriptionally upregulated in DT/DF and modulated with sorafenib.

### 10.3.4 A091105-ST1 Biopsies

#### Pre- and day 8 (+ 7 days) post-randomization biopsy guidelines

A091105-ST1 must be offered to all patients enrolled on A091105 (although patients may opt to not participate). Patients who consent to A091105-ST1 will undergo 2 biopsies (pre-treatment and day 8 post-randomization).

The following exploratory studies will be performed and analyzed in the laboratory of [name], correlative chair. Bio-informatics analysis will be provided by MSKCC Bio-informatics core lab. Blood, pre-treatment and day 8 matched tumor biopsies are required elements of this study for patients. Patients will undergo 2 biopsies (procuring 5 cores for each biopsy) by interventional radiology under image guided CT or U/S. Core biopsies will be evaluated for the following studies: 1) one core will be formalin fixed for pathological studies and TMA construction, 2) 1 - 2 cores will be used for gene array expression profiling to determine a sorafenib signature of response, whole exome sequencing, microRNA array and epigenetics 3) one core will be used for a constrained evaluation of phospho-proteomic changes utilizing a Zaptosens reverse protein array of selected pathways identified from genetic studies.

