### 2.3 Correlative Companion Study Objectives

- 2.3.1 To evaluate changes in MRI T2 to predict (or correlate) with a biological effect such as tumor growth (by RECIST v1.1), and pain palliation.
- 2.3.2 The mechanism of action of sorafenib in DT/DF remains unknown. In patients consenting to undergo the paired tumor biopsies (A091105-ST1), treatment induced changes will be quantified by histology, gene expression profiling, proteomic changes and selected interrogation of key pathways by Western blot and RT-PCR.
- 2.3.3 To collect archival tissue, baseline (tumor, blood) and day 8 (tumor, blood) specimens for basic science research (A091105-ST1).
- 2.3.4 To assess patient-reported adverse events and quality of life (QOL) as measured by the PRO-CTCAE and the single-item overall LASA (A091105-HO1).
- 2.3.5 To assess pain palliation measured by the “worst pain” item of the Brief Pain Inventory Short Form (A091105-HO1).

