### 6.3 Specimen Submission

| Specimen                                     | Baseline  | Cycle 1, Day 8
(+7 days) | Location |
|----------------------------------------------|-----------------------|-----------------------------|----------|
| Archival tissue block
(FFPE)  | X                     |                             | OSU      |
| Peripheral whole
blood        | X                     | X                           | OSU      |
| Research tumor
biopsy         | X                     | X                           | OSU      |
| Plasma                           | X                     | X                           | OSU      |

1 Required for all patients registered to A091105. For patients who consent to A091105-ST1, this tissue block will also be used for study described in [Section 10.3](#)

2 For patients consenting to optional study A091105-ST1

3 Obtain prior to the start of protocol treatment and between days 8 and 11 of Cycle 1

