| Pregnancy Test (serum) B                                                                                    | X (4)                  |                                                             |                                                                 |                                          |
| Na, K, chloride, bicarb, BUN, creatinine, glucose, Ca, SGOT (AST), SGPT (ALT), bili, total protein, albumin | X                      | X                                                           | X, C                                                            |                                          |
| Staging                                                                                              |                        |                                                             |                                                                 |                                          |
| Spiral CT Scan or MRI of lesion                                                                             | X(7)                   |                                                             | A(7)                                                            | B                                        |
| Companion Studies                                                                                    |                        |                                                             |                                                                 |                                          |
| QOL Assessments                                                                                             | X (3)                  | X (3)                                                       | X (3)                                                           |                                          |
| Archival Block                                                                                              | X (5)                  |                                                             |                                                                 |                                          |
| Tumor Biopsy and blood†                                                                                     |                        |                                                             | See Section 6.3                                                 |                                          |

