## 8.0 TREATMENT PLAN

Protocol treatment is to begin within 14 days of randomization. One cycle is equal to 28 days.

Questions regarding treatment should be directed to the Alliance Study Chair.

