### **Core #5**

Biopsies will be descriptive and comment on 1) proliferation (Ki-67 expressed as percentage) to assess treatment response (pre-treatment base line and post therapy for drug effect) and expressed as percentage of tumor cells as <10%, 10-25%, 25-50% and >50%, 2) degree of fibrosis, 3) changes in vascularity, 4) necrosis and 5) ratio of nuclear to cytoplasmic beta catenin.

For TMA construction, the techniques are previously well described by Lazar and colleagues. Hematoxylin and eosin (H&E) stained sections will be reviewed to define areas of desmoid tumor; dermal scars, reactive tissue and solitary fibrous tumor will serve as controls. Using an automated TMA apparatus (ATA-27; Beecher Instruments, Sun Prairie, WI), 0.6-mm punch samples (two per case) will be obtained along with controls and formatted into three recipient blocks. H&E-staining of 4-micron TMA sections will be used to verify all samples.

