#### **BLINDED (Sorafenib or Placebo) THERAPY (Active and Placebo Arms)**

**No blinded starter supplies will be available for this study.** Blinded, patient specific supplies will be sent to the registering investigator at the time of randomization and should arrive within 7 to 10 days. Randomization will be performed by the ALLIANCE Statistics and Data Center. The assigned ALLIANCE patient ID number must be recorded by the registering institution for proper bottle dispersion. Once a patient has been registered with

the ALLIANCE Statistics and Data Center, the ALLIANCE Statistics and Data Center will electronically transmit a clinical drug request for that patient to the PMB. This request will be entered and transmitted by the ALLIANCE Statistics and Data Center the day the patient is registered and will be processed by the PMB the next business day and shipped the following business day. Shipments within the United States will be sent by FedEx Ground (delivery within 5 days). Thus, if a patient is registered on Monday, ALLIANCE would enter a clinical drug request for that patient on Monday and PMB would process that request on Tuesday and ship the drug on Wednesday. United States sites could expect to receive their order approximately Tuesday or Wednesday. Shipments to United States sites can be expedited (i.e., receipt on Thursday in example above) by the provision of an express courier account name and number to the ALLIANCE Statistics and Data Center at the time the patient is randomized.

The initial request will be for **1 – 140 tablet bottle (a 2 cycle / 8 week supply)** at a dose of 400 mg [2 \* 200 mg tablets] orally once daily) of sorafenib or matching placebo. Six (6) weeks after the initial electronic request (i.e., 2 weeks before the next bottle is needed), sites may reorder an additional **1 – 140 tablet bottle (a 2 cycle / 8 week supply)** by submitting an agent request through the PMB Online Agent Order Processing (OAOP) application (<https://eapps-ctep.nci.nih.gov/OAOP/pages/login.jspx>). Access to OAOP requires the establishment of a CTEP Identity and Access Management (IAM) account (<https://eapps-ctep.nci.nih.gov/iam/>) and the maintenance of an “active” account status and a “current” password. Once a CTEP IAM account has been established, go to

<https://eapps-ctep.nci.nih.gov/OAOP/pages/login.jspx> to access the OAOP application.

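### Section 10.3.4 times the second ST1 biopsy from randomisation, against the Cycle 1 clock in Section 6.3, and so permits a second biopsy before any drug when the first dose is on day 9 or later

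*Combined protocol and SAP*

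**What the plan says.** Section 10.3.4 uses the randomisation clock twice. The heading reads "Pre- and day 8 (+ 7 days) post-randomization biopsy guidelines", and the text reads "Patients who consent to A091105-ST1 will undergo 2 biopsies (pre-treatment and day 8 post-randomization".

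Section 6.3 uses the treatment clock. Its table column for the second sample is Cycle 1, Day 8 with a 7-day allowance. Footnote 3 is narrower: "Obtain prior to the start of protocol treatment and between days 8 and 11 of Cycle 1". In the Section 7.0 calendar, the tumour biopsy row says only "See Section 6.3". Nothing states which section prevails if the two disagree.

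Two other provisions separate the clocks. Section 8.0 says "Protocol treatment is to begin within 14 days of randomization". Section 11.2.2 says there are no blinded starter supplies and that patient-specific drug is sent "at the time of randomization and should arrive within 7 to 10 days".

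The purpose is clear. Under the Section 2.3 objectives, "treatment induced changes will be quantified by histology, gene expression profiling, proteomic changes", and the Core #5 text describes the pair as "pre-treatment base line and post therapy for drug effect".

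**The concern.** If dosing began on the day of randomisation, the two clocks would nearly coincide. Under this protocol's supply arrangements it usually cannot: the drug is expected a week or more after randomisation. Day 8 after randomisation may therefore come before the patient has taken a tablet.

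A pair with both biopsies taken before drug says nothing about the effect of sorafenib. As Section 15.3.3 is written, such a pair would still enter the microarray comparison and the paired t-test on protein levels, because that section has no check that a dose preceded the second sample. The patient would also have undergone a second five-core biopsy that could not answer the question it was taken for.

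**Working it through.** The plan states no figure on this point, so there is none to reproduce. The check is a day count.

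**Inputs and conventions**
- Randomisation is day 0. The first dose is on day d, with d from 0 to 14 (Section 8.0).
- Cycle 1 Day 1 is the day of first dose. The protocol does not define this expressly; it follows from Section 6.2, which equates weeks of treatment with cycle days.
- Section 10.3.4 window: days 8 to 15, which is 8 days.
- Section 6.3 table window: Cycle 1 Days 8 to 15, which is d + 7 to d + 14.
- Section 6.3 footnote 3 window: Cycle 1 Days 8 to 11, which is d + 7 to d + 10.
- Expected drug arrival: days 7 to 10 (Section 11.2.2). For these days, assume the first dose is taken on arrival.

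**Formulas**
- Section 10.3.4 window days before the first dose: max(0, d − 8).
- The Section 10.3.4 and Section 6.3 windows share a day only if d + 7 ≤ 15, that is, d ≤ 8. The condition is the same for footnote 3, because both Section 6.3 windows open at d + 7.

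**Results**

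| First dose, day d | Section 10.3.4 window days before / on / after first dose | Section 6.3 table window | Days satisfying both |
|---|---|---|---|
| 7 | 0 / 0 / 8 | 14–21 | 14, 15 |
| 8 | 0 / 1 / 7 | 15–22 | 15 |
| 9 | 1 / 1 / 6 | 16–23 | none |
| 10 | 2 / 1 / 5 | 17–24 | none |
| 12 | 4 / 1 / 3 | 19–26 | none |
| 14 | 6 / 1 / 1 | 21–28 | none |

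On two of the four expected arrival days (9 and 10), no date satisfies both sections. If a site follows the body text and takes the biopsy exactly on day 8, arrival on days 7 to 10 places it from 1 day after (8 − 7) to 2 days before (8 − 10) the first dose.

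Since d is at most 14, day 15 always falls after the first dose. Section 10.3.4 therefore never forces a pre-drug biopsy.

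**Sensitivity to the day count.** If randomisation is called day 1, the latest first dose is day 15. The day 9 threshold is unchanged. In that extreme case 7 of the 8 window days precede the first dose and the eighth is the dose day.

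**Under Section 6.3 alone**, the second biopsy always falls 7 to 14 days after first dose by the table, or 7 to 10 days by footnote 3. It can never precede drug.

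**The case against.** The strongest reply is that sites are already sent to the right place. The calendar refers only to Section 6.3, and Section 10.3.4 is mostly laboratory methods. A site that follows the calendar takes the biopsy on the Cycle 1 clock and never has to satisfy both sections. This stands, and it is the main reason the point is minor. It does not remove the conflict: Section 10.3.4 presents itself as biopsy guidelines, and no text ranks it below Section 6.3.

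It can also be said that a pre-drug second sample is a strained reading. Section 10.3.4 sets day 8 against pre-treatment, Core #5 speaks of drug effect after therapy, and Section 15.1.1 refers to biopsies while patients are receiving treatment on placebo. The intent is indeed plain. The instruction as written still counts from randomisation, in both heading and text.

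The two-in-four figure counts calendar days, not patients. Section 11.2.2 also offers expedited shipping, under which a Monday registration gives receipt on Thursday, day 3; dosing on receipt would then leave no pre-drug window days. Both remarks are right. The standard example in the same section, however, has a Monday registration received about the Tuesday or Wednesday of the next week, day 8 or 9, so a day 9 start is ordinary.

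Finally, confirming that a dose came before a post-treatment sample may be called routine data cleaning. That is fair as a description of good practice, but where the protocol carries two incompatible clocks it is better to write the check down.

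**Conclusion.** The concern holds, as a minor error in the plan as written. Section 10.3.4 and Section 6.3 use different clocks. When the first dose is on day 9 or later, part of the Section 10.3.4 window precedes any drug and no date meets both sections. The share of window days before drug runs from 1 of 8 for a day 9 start to 6 of 8 for day 14, the latest allowed, with randomisation as day 0.

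This rests on taking Cycle 1 Day 1 as the first dose and, for the expected arrival days, on dosing on arrival. The day 9 threshold does not depend on whether randomisation is day 0 or day 1.

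The consequence is confined to an optional, exploratory substudy; no primary or secondary endpoint is affected. The documents do not show whether any site worked from Section 10.3.4, or how many pairs were affected, so no dilution of the treatment-change estimate can be given.

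**What to change.** **Wording.** In the heading and text of Section 10.3.4, replace the post-randomisation timing with *Cycle 1 Day 8 (+7 days), counted from first dose*. Align Section 6.3 footnote 3 to the same window, Cycle 1 Days 8 to 15, since it now disagrees with its own table. This is probably moot for new biopsies: patients were unblinded on November 17, 2017 (Section 15.1), the update summary says placebo is no longer used, and Section 7.0 does not require these biopsies after crossover.

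**Analysis.** This step still matters for specimens already collected. In Section 15.3.3, derive days on study drug at the second biopsy as the specimen procurement date minus the first-dose date. Report the distribution by arm, and leave pairs with no dose before the second biopsy out of the treatment-change analysis.

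**Cost.** One derived variable and a short wording change in two sections, with no added procedure. Section 6.3.5 requires the procurement date on every specimen label. Section 8.1 asks patients to record daily doses in a diary, and the Appendix VI form has a field for the treatment start date. That form is titled optional, so the availability of the first-dose date in the study database should be confirmed. The downside is the possible loss of a few pairs, none of which could have shown a drug effect.
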